We propose a 3 month RCT pilot of alcohol biosensor monitoring (ABM)(WrisTAS-see methods) for patients with a recent hospital discharge for ALD decompensation. Patients who intend to stop drinking will wear the ABM and be randomized to receive ABM personalized feedback on the data retrieved from the device (ABM) vs. an enhanced usual care group that will wear the ABM device but not receive information about device data (EUC). Considering future translation into medical practice we chose a monthly assessment schedule aligned with the typical ALD clinical follow up and chose the EUC group to most closely resemble a typical medical encounter where generic questions on alcohol use are asked. The study will also include quantitative and qualitative data collected from participants and 15 clinical stakeholders (e.g. physicians, nurse practitioners, care coordinators) who will provide opinions on ABM usability, acceptability, feasibility, and potential to change clinical care and outcomes. Qualitative methods are especially useful for understanding patient and clinician cultures and perspectives to determine the perceived needs, barriers, and preferences for monitoring alcohol use and are essential for future translation of this technology into clinical practice.

Specific Aim 1. To determine usability, acceptability, feasibility and efficiency of ABM for ALD patients.

Specific Aim 2. To determine whether ABM plus feedback improves outcomes for ALD patients who intend to stop alcohol use compared to EUC. Hypotheses 1-5: ABM will 1) reduce alcohol use (primary outcome), and 2) improve readiness for alcohol abstinence, 3) improve self-efficacy, 4) improve initiation of addiction treatment and 5) reduce ALD related hospital admissions and ER visits (secondary outcomes).

Specific Aim 3. To explore with clinicians whether ABM data is useful, acceptable, feasible and efficient.

This study will inform our development of a full scale project by 1) determining the potential for and value to ABM healthcare integration 2) identifying barriers to ABM implementation 3) determining long term wearability of ABM devices and 4) determine whether identified patient outcome effect sizes appear clinically meaningful to justify ABM monitoring and evaluation in a full-scale randomized controlled trial in the clinical environment.

D. Approach: Research Design and Methods

We address the NIH mandate for rigor and transparency (NOT-OD-16-011) in the proposal and Table 1.

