The primary outcome is alcohol use (H1), which we will test via 2 measures: % of days drinking; total quantity/frequency during period between downloads. Secondary outcomes (**H2-4**) are readiness for alcohol abstinence, self-efficacy, initiation with addiction treatment will be analyzed using SOCRATES subscales and AASE/AWR (continuous variables), **H5** Form 90AF hospital stays and ER visits (% of days hospitalized and no. of hospital admissions+ER visits). For each primary/secondary outcome, we will use a linear mixed effects model with fixed effects for intervention group (2 groups) and the repeated measures factor, time (pre-intervention, 6 weeks, and 3 mons post-intervention); and random effects for individual participant and intercept.

Statistical Power: Ours is an exploratory study; the ESs we might observe are unknown. For the simple effects we will compute as described above, with 30 participants in each of 2 groups being compared in a given test and alpha at .05, we would have power at 80% to detect an ES, $d \geq 0.76$. Brief feedback interventions can produce moderate to large ESs for reducing alcohol use and consequences (d of 0.6-0.8).^{81,111-113} Even if 5-8 participants are lost to attrition, we should have sufficient power to detect simple effects within the range found in previous feedback studies. Again, however, our interest will be to examine feasibility issues and ESs as opposed to testing for statistical significance.

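### The attrition sentence overstates power: after 5-8 losses in total, a simple comparison reaches 80% power only from d = 0.77-0.79, the top edge of the cited 0.6-0.8 range

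*Combined protocol and SAP*

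**What the plan says.** All the figures stand in section E, Analytic Plan, under Statistical Power.

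- **Base case.** "with 30 participants in each of 2 groups being compared in a given test and alpha at .05", the plan says "we would have power at 80% to detect an ES" of d = 0.76 or more.
- **Benchmark.** "Brief feedback interventions can produce moderate to large ESs for reducing alcohol use and consequences (d of 0.6-0.8").
- **Attrition.** "Even if 5-8 participants are lost to attrition", the plan continues, "we should have sufficient power to detect simple effects within the range found in previous feedback studies".
- **Status of testing.** The paragraph calls the study exploratory and closes by saying that "our interest will be to examine feasibility issues and ESs as opposed to testing for statistical significance".

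The Specific Aims section says that one purpose of the pilot is to "determine whether identified patient outcome effect sizes appear clinically meaningful to justify ABM monitoring" in a full-scale trial.

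The plan does not recompute the detectable effect after attrition, say whether 5-8 is a total or a number per arm, or state whether alpha is one- or two-sided.

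**The concern.** The plan's own threshold of 0.76 lies near the top of the 0.6-0.8 range. By the plan's 80% standard, effects from 0.60 to 0.75 are already short of power with nobody lost, and losses can only raise the threshold. The attrition sentence nevertheless presents 5-8 losses as harmless and refers to the cited range without restriction.

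What is at stake is interpretation. A reader who accepts that power was sufficient for 0.6-0.8 could take a non-significant pilot result, by itself, as evidence against effects of that size. For much of that range the design cannot support this.

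**Working it through.** **Inputs.** From Statistical Power: 30 per group, alpha 0.05, 80% power, stated threshold d = 0.76, cited range 0.6-0.8, 5-8 lost. From the study design text: 1:1 allocation.

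**Assumptions.** Two-sided test; unadjusted two-sample t-test; lost participants contribute no data. Two-sided is assumed because a one-sided test with 30 per group would give a threshold of 0.65, far from the stated 0.76.

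**Formula.** Power = P(|T| > t(0.975, df)), where T is noncentral t with df = n1 + n2 - 2 and noncentrality d × √(n1·n2/(n1 + n2)). The threshold is the d at which power equals 80%.

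**Step 1: reproduce the plan's figure.** For 30+30, √(900/60) = 3.873. At d = 0.76 the noncentrality is 0.76 × 3.873 = 2.94, the critical value is 2.002 and power is 82.5%. The exact 80% threshold is 0.736. So 0.76 is sound and slightly conservative; 29 per arm would suffice for it.

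**Step 2: apply the stated losses.**

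| Analysed | Reading | 80% threshold | Power at 0.6 | at 0.7 | at 0.8 |
|---|---|---|---|---|---|
| 30+30 | no loss | 0.736 | 62.8% | 76.0% | 86.1% |
| 28+27 | 5 lost in total | 0.770 | 58.9% | 72.2% | 82.9% |
| 26+26 | 8 lost in total | 0.792 | 56.4% | 69.7% | 80.7% |
| 25+25 | 5 lost per arm | 0.809 | 54.7% | 67.9% | 79.1% |
| 22+22 | 8 lost per arm | 0.865 | 49.4% | 62.1% | 73.6% |

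Example for 28+27 at d = 0.6: √(756/55) = 3.708, noncentrality 2.22, critical value 2.006, power 58.9%.

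**Step 3: sensitivity.**
- If all losses fall in one arm, the threshold is 0.773 (30+25) to 0.802 (30+22).
- Rescaling the plan's own 0.76 gives 0.76 × √(60/55) = 0.794 and 0.76 × √(60/52) = 0.816.
- For 80% power, d = 0.6 needs 45 analysed per arm and d = 0.7 needs 34.
- The Sample text reports 80-90% retention in earlier cohorts, which is 6-12 lost of 60. At 12 lost (24+24) the threshold is 0.826.

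**Step 4: what a non-significant result could say.** The smallest significant observed d is t(0.975, df) × √(1/n1 + 1/n2): 0.541 for 28+27 and 0.557 for 26+26. The approximate 95% CI half-width is 1.96 × √(1/n1 + 1/n2 + d²/(2(n1 + n2))).
- An observed d of 0.5 has half-width 0.537 (28+27) or 0.552 (26+26). The interval is -0.04 to 1.04 or -0.05 to 1.05, which contains the whole cited range.
- An observed d of 0 has half-width 0.529 or 0.544, so the interval excludes the whole cited range.
- The upper limit falls below 0.6 when the observed d is below about 0.07 (28+27) or 0.06 (26+26), and below 0.8 when it is below about 0.27 or 0.25.

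Some non-significant results are therefore uninformative about 0.6-0.8 and others are not. The interval decides, not the p-value.

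**The case against.** **Literal wording.** Thresholds of 0.77-0.79 do lie inside 0.6-0.8, and the plan prints 0.76 next to that range, so nothing is hidden. This stands as far as it goes: the fault is overstatement. A reader might infer that the plan's calculation is wrong. It is not; 0.76 is slightly conservative. But the unrestricted sentence will be read as covering the range, and by the plan's own 80% standard it does not.

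**Exploratory purpose.** The same paragraph puts effect sizes ahead of significance, and the Specific Aims tie the full-scale decision to effect sizes. This also stands, and it limits the consequence. It does not make the power statement accurate.

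**The planned analysis may do better.** The plan specifies a linear mixed model over three time points, and someone lost after the 6-week assessment would still contribute data. So treating every loss as wholly missing is a worst case for that model. The gain cannot be credited in numbers, however. The plan gives no correlation and does not say which contrast carries the test. Adjusting for baseline as a covariate would scale the threshold by √(1 - ρ²), but the plan makes baseline a level of the time factor. A change-from-baseline contrast scales by √(2(1 - ρ)), which is worse than the unadjusted comparison when ρ is below 0.5. The power sentence itself concerns simple effects, and 0.76 shows no such gain.

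**Recruitment margin.** The Sample text's 4-5 enrollees a month over 15 months gives 60-75 people. With 75 enrolled and 5-8 lost, 67-70 would remain and the threshold would be about 0.69-0.68, still well above 0.6. The power paragraph does not rely on this margin.

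**Conclusion.** The point holds as an overstated power claim. With 5-8 lost in total, 80% power starts at d = 0.77-0.79, so only the top edge of 0.6-0.8 is covered; power is 59-56% at the lower end. With 5-8 lost per arm the threshold is 0.81-0.87 and none of the range is covered. These figures rest on a two-sided 0.05 test, a simple unadjusted comparison of 30 per group before losses, and no data from those lost.

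A reader might go further in two ways that the documents do not support. One is that a go/no-go decision is compromised: no decision rule in the plan depends on significance. The other is that no non-significant result could count against 0.6-0.8: an observed d near zero would have a 95% CI excluding that range.

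**What to change.** Replace the attrition sentence with text such as:

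> If 5-8 participants in total are lost, a simple unadjusted two-group comparison (two-sided 0.05) has 80% power for d ≥ 0.77-0.79, that is, only the top of the 0.6-0.8 range; power is 59-56% at d = 0.6 and 83-81% at d = 0.8. Effect sizes will be reported with 95% CIs (half-width about 0.5-0.6). A non-significant result will be interpreted from its CI, not taken by itself as evidence against effects of 0.6-0.8.

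In addition:
- State whether 5-8 is a total or per arm. If per arm, use 0.81-0.87, with power 55-49% at d = 0.6 and 79-74% at d = 0.8.
- The 0.76 may stay if it is labelled conservative (exact threshold 0.74).
- If credit is taken for repeated measures or baseline adjustment, name the contrast and the assumed correlation.

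The cost is a few sentences and a less favourable stated power. Enrolment, the analysis model and the decision criteria do not change.
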